### 6.8.1. Rescue Medicine

The study site will not supply any form of study specific rescue medication. However, participants will be prescribed hydrocortisone for intramuscular use as per standard care, for use in case of an adrenal crisis. Occurrence of adrenal crisis will be documented at each study visit in the study-specific form. An adrenal crisis leading to admission will be registered as a SAE.

© 2015-2021 TransCelerate BioPharma

Doc. No. CT 2.01.01. Valid from 31 Jan 2022. Only the electronic version is valid.

Page 27 of 65

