# 7.2. Participant Discontinuation/Withdrawal from the Study

- A participant may withdraw from the study at any time at the participant's own request for any reason (or without providing any reason).
- A participant may be withdrawn at any time at the discretion of the investigator for safety reasons.
- At the time of discontinuing from the study, if possible, an early discontinuation visit should be conducted, as shown in the SoA. See SoA for data to be collected at the time of study discontinuation and follow-up and for any further evaluations that need to be completed.
- The participant will be permanently discontinued from the study intervention and the study at that time.
- If the participant withdraws consent for disclosure of future information, the sponsor may retain and continue to use any data collected before such a withdrawal of consent.
- If a participant withdraws from the study, the participant may request destruction of any samples taken and not tested, and the investigator must document this in the site study records.

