### **8.2.1.** Patient Reported Outcome (PROMs)

- Two HRQoL will be sampled at baseline and after 1, 6 and 12 months; the generic questionnaire RAND-36 and the PAI-specific questionnaire AddiQoL. RAND-36 is thoroughly validated and extensively used and suitable both for comparison of HRQoL scores between PAI and healthy controls, and for comparing score between PAI and other disease groups (20). The AddiQoL is developed and thoroughly validated by us as a PAI-specific HRQoL instrument, more sensitive for detecting changes in HRQoL over time in PAI (21).
- For evaluation of sleep, Sleep Diary will be sampled at visit 5-6.
- Working ability (i.e. sick leave, sick pension) will be registered at each visit (NOKLUS study form).
- Cognitive test administration using Memoro, a web-based cognitive test platform developed by [name] and [name], NTNU (28-30). The test can be run on a computer, tablet, or smartphone. Participants receive links via sms, e-mail, as a printed pdf (letter) or through helsenorge.no. Memoro uses same encryption as online banking (nettbanken) and has ROS analysis approving the system. The server is located at NTNU's central server location. No clinical data is stored only the test scores. Some background variables are stored to provide norm data for references (year born, education level according to groups (vgs., bachelor, master or above) and handedness). Participants can receive their scores relative to the norm data if that is of interest. Score will be transferred directly to TSD or similar server at UiT/Haukeland or via encrypted file sender. The cognitive tests that will be used have been used in many other studies (incl. HUNT and MoBa) and have therefore system norms as a reference.

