## 8.4.1. Time Period and Frequency for Collecting AE and SAE Information

All SAEs and AEs will be collected from the start of study intervention until visit 6 at the time points specified in the SoA (Section 1.3).

All SAEs will be recorded and reported to the sponsor or designee immediately and under no circumstance should this exceed 24 hours, as indicated in Appendix [3/7]. The investigator will submit any **updated SAE data to the sponsor within 24 hours** of it being available.

Investigators are not obligated to actively seek information on AEs or SAEs after conclusion of the study participation. However, if the investigator learns of any SAE, including a death, at any time after a participant has been discharged from the study, and the investigator considers the

© 2015-2021 TransCelerate BioPharma

Doc. No. CT 2.01.01. Valid from 31 Jan 2022.

Only the electronic version is valid.

Page 39 of 65

event to be reasonably related to the study intervention or study participation, the investigator must promptly notify the sponsor.

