## 8.4.3. Follow-up of AEs and SAEs

After the initial AE/SAE report, the investigator is required to proactively follow each participant at subsequent visits/contacts. All SAEs will be followed until resolution, stabilization, the event is otherwise explained, or the participant is lost to follow-up (as defined in Section 7.3). Further information on follow-up procedures is provided in Appendix 3.

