## 10. Supporting Documentation and Operational Considerations

# 10.1. Appendix 1: Regulatory, Ethical, and Study Oversight Considerations

The study will be performed in accordance with the protocol, the World Medical Association Revised Declaration of Helsinki (2008), the ICH Harmonized Tripartite Guideline for Good Clinical Practice, and any local regulations. The Ethics committee for medical research, Western Norway has granted permission to conduct the trial (ADNorGC). The patient will receive oral and written information concerning the study.

ROAS have ethical approval (REK 2013/1504) and is licensed by the Norwegian Data Protection Authority (1). This specific project was submitted to IEC in mid-2021, and an ethical approval has been obtained. Likewise, the project will be registered in the ClinicalTrials.gov database prior to study start.

All participants will receive thorough oral and written information before providing written consent for study participation. The participants are free to withdraw their consent at any time during the study. Clinical records and results will be archived in hospital records. Data will be collected to computerized research files without patient identifiers and stored according to the hospitals' research ethics guidelines. Biological research materials (blood samples) are coded and stored at laboratory at Haukeland University Hospital according to general regulations, D

Patients will be instructed to report any adverse events during the study period to the recruiting physician. If a patient develops conditions meeting the exclusion criteria or serious adverse events, the patient will be withdrawn from the study. The recruiting physician may also discontinue study participation at any time if it is considered necessary for any of the following reasons:

- Significant protocol deviation or violation.
- Significant failure to comply with study requirements.

Deviation log: We encourage doctors in charge of patients to report all deviations in the protocol to the coordinating investigator or medical monitor, as well as to register in the patient journal.

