### c. Requires inpatient hospitalization or prolongation of existing hospitalization

• In general, hospitalization signifies that the participant has been admitted (usually involving at least an overnight stay) at the hospital or emergency ward for observation and/or treatment that would not have been appropriate in the physician's office or outpatient setting. Complications that occur during hospitalization are AEs. If a complication prolongs hospitalization or fulfills any other serious criteria, the event is serious. When in doubt as to whether hospitalization occurred or was necessary, the AE should be considered serious.

© 2015-2021 TransCelerate BioPharma

Doc. No. CT 2.01.01. Valid from 31 Jan 2022. Only the electronic version is valid.

Page 53 of 65

• Hospitalization for elective treatment of a pre-existing condition that did not worsen from baseline is not considered an AE.

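### Appendix 1 makes withdrawal from the study mandatory after any serious adverse event, while section 7.2 leaves it to the investigator; where Appendix 1 is followed, later HRQoL scores and the active search for new safety events are lost

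*Protocol*

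**What the plan says.** Appendix 1 (section 10.1) states: "If a patient develops conditions meeting the exclusion criteria or serious adverse events, the patient will be withdrawn from the study". It sets no limit by relatedness, severity or judgement. Its next sentence then gives the recruiting physician an option to end participation for other reasons, so the SAE rule reads as mandatory by contrast.

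Section 7.2 is permissive: "A participant may be withdrawn at any time at the discretion of the investigator for safety reasons". It also defines what withdrawal means: "The participant will be permanently discontinued from the study intervention and the study at that time". One early discontinuation visit is foreseen, where feasible.

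The trigger is broad. Section 10.2.2 counts as serious any event that "Requires inpatient hospitalization or prolongation of existing hospitalization", and section 6.8.1 adds: "An adrenal crisis leading to admission will be registered as a SAE".

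On follow-up, section 8.4.3 says: "After the initial AE/SAE report, the investigator is required to proactively follow each participant at subsequent visits/contacts". It also has every SAE followed to resolution, stabilisation or another explanation, or until the participant is lost to follow-up. Section 8.4.1 collects events up to visit 6, but says: "Investigators are not obligated to actively seek information on AEs or SAEs after conclusion of the study participation".

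For the primary endpoint, section 8.2.1 says: "Two HRQoL will be sampled at baseline and after 1, 6 and 12 months". Section 3 lists differences in adverse events, serious adverse events and adrenal crises as safety endpoints.

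**The concern.** Two rules in one protocol give different answers when a participant has a serious adverse event, and nothing ranks them. Sites could handle the same event differently.

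Where Appendix 1 is applied, the participant leaves both drug and study. No section provides for HRQoL collection after the early discontinuation visit. The missing primary-endpoint data then depend on something that happens after randomisation and that treatment may influence. If one arm has more SAEs, more of its later scores are missing, and its time under active safety observation is shorter. A first admitted adrenal crisis would end the active search for a second in that participant.

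The rule has no stated safety purpose. Section 7.1 says that replacement is needed throughout and lets the investigator choose another glucocorticoid, without linking that change to leaving the study.

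**Working it through.** **1. The passages side by side**

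| Question | Appendix 1 (10.1) | Elsewhere |
|---|---|---|
| SAE occurs: withdraw? | Yes, always | 7.2: investigator may, for safety |
| Effect of withdrawal | Leaves the study | 7.2: leaves drug and study |
| Triggering SAE | Not addressed | 8.4.3: followed to resolution or stabilisation |
| New events afterwards | Not addressed | 8.4.1: no duty to seek them; related SAEs that come to light must still be notified |
| HRQoL afterwards | Not addressed | 7.2: early discontinuation visit only, where feasible |

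**2. The plan's own figure**

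Section 9.3 uses n = 2 × (SD/difference)² × k per group, with SD 4 and difference 4. For two-sided 5% and 90% power the exact k is 10.51, so n = 2 × 1 × 10.51 = 21.01. This agrees with the stated 21; the printed k of 10.9 would give 21.8. With 10% drop-out, 42 × 1.1 = 46.2, against the stated 46. About 50 are planned.

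**3. Data lost where Appendix 1 is followed**

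Assumptions: 50 patients, SAE share s (no rate is given in the protocol), first SAE uniform over 12 months, no other drop-out. Month-12 scores lost = 50s. Month-6 scores lost = 25s. Active observation lost = 50s × 6 of 600 person-months.

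| s | Month 12 lost | Month 6 lost | Person-months lost |
|---|---|---|---|
| 5% | 2.5 | 1.25 | 15 (2.5%) |
| 10% | 5 | 2.5 | 30 (5%) |
| 20% | 10 | 5 | 60 (10%) |

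**4. Month-12 power under the planned type of analysis**

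Section 9.1 names a linear mixed model. Assumptions: N = 50, difference 4, SD 4 read as the SD of a single score, common baseline mean, equal correlation r between visits, 10% lost after baseline, SAE withdrawals on top with uniform timing, normal approximation.

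With no SAE withdrawals, 45 have a month-12 score and the standard error is 4 × √[(4/45)(1 − r²)].
- r = 0.5: 4 × √(0.0889 × 0.75) = 1.033. Then 4/1.033 − 1.96 = 1.91, so power is 97.2%.
- r = 0.3: 4 × √(0.0889 × 0.91) = 1.138. Then 4/1.138 − 1.96 = 1.56, so power is 94.0%.

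With SAE withdrawals, the month-12 count is 45(1 − s). The full model also uses the month-1 and month-6 scores recorded before the SAE.

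| s | r = 0.5 | r = 0.3 |
|---|---|---|
| 0 | 97.2% | 94.0% |
| 5% | 96.6% | 93.0% |
| 10% | 95.9% | 91.7% |
| 20% | 94.0% | 88.6% |

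Hand check at s = 20%, r = 0.5, using baseline and month 12 only: 4 × √[(4/36) × 0.75] = 1.155, and 4/1.155 − 1.96 = 1.50, or about 93%. The earlier visits raise this slightly, to 94.0%.

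**5. Possible bias at month 12**

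If an SAE lowers HRQoL lastingly by f points and the fall is never observed, the hidden arm difference is (difference in SAE share) × f. For 10% v 20% and f = 4: 0.10 × 4 = 0.40 points. For 10% v 15% and f = 2: 0.05 × 2 = 0.10 points. With equal shares and equal falls it is zero. Against the no-SAE standard error of 1.033 to 1.138, 0.40 points is roughly 0.35 to 0.39 of a standard error, and 10% of the 4-point target.

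**The case against.** The strongest reply is that section 7.2 never mentions SAEs. It gives a general permission, and a specific SAE rule can sit beside it. That softens the conflict but does not remove it: an investigator with discretion over safety withdrawal has none left for the events where it matters most, and no precedence is stated.

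Three stronger readings are tempting, and the documents do not support them.

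- **Appendix 1 flatly contradicts section 8.4.3.** It does so only in part. Following the triggering SAE at later contacts does not require study membership. Only the expectation of following each participant at subsequent visits sits badly with mandatory withdrawal.
- **The safety comparison is lost.** The triggering SAE, including an admitted adrenal crisis, is already recorded and is followed. The proportion of patients with at least one SAE is therefore largely preserved. What is lost is the active search for later events in the same patients.
- **Power falls well below target.** A completer t-test at month 12 (difference 4, SD 4) gives 90.6% with 45 evaluable and 83.0% with 36. That test ignores the baseline, month-1 and month-6 scores, whereas section 9.1 plans a mixed model that uses them.

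It is also fair to say that sections 9.2.1 and 9.2.2 foresee sensitivity analyses for missing data. They are conditional on the missing data being judged influential, they rest on assumptions, and they cannot recover visits that never took place.

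**Conclusion.** The point holds as an inconsistency in a conduct rule, with a data loss that is avoidable wherever Appendix 1 is followed. It should be fixed, but it does not threaten the trial.

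The wording conflict with section 7.2 is certain. The size of the consequence is not known, because the protocol gives no SAE rate and sites may apply section 7.2 instead. Under the assumed SAE shares of 5% to 20%, month-12 power falls by at most about 3 percentage points at correlation 0.5 and about 5 at correlation 0.3. It drops below 90% only at the 20% share with the lower correlation. These levels depend on reading SD 4 as the SD of a single score and on a common baseline mean. Without the latter they lie nearer the completer figures.

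The bias illustration needs unequal SAE shares and a lasting, unobserved fall in HRQoL. Even then it stays at or below 0.40 points. The principle matters more than the size: whether a participant is observed should not depend on an outcome that treatment may affect.

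**What to change.** - **Appendix 1:** delete the SAE trigger from the sentence and refer to section 7.2.
- **Section 7.2:** add that an SAE alone is not a reason for withdrawal from the study. A participant who has an SAE, or who stops the assigned drug, keeps the scheduled HRQoL, AE/SAE and adrenal-crisis assessments to month 12, unless consent is withdrawn or the investigator withdraws the participant for safety under the existing rule. The second exception keeps the investigator's discretion intact.
- **Remaining trigger in Appendix 1:** in the same edit, say whether a participant who newly meets an exclusion criterion stops only the study drug or also leaves follow-up. Otherwise the two sentences will collide. Cancer is an example of an SAE in section 10.2.2, and treatment for active malignancy is an exclusion in section 5.2. Pregnancy leads to withdrawal from the study in section 8.3.4 but not to stopping study treatment in section 8.4.5.

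The cost is a short protocol amendment with the ethics and, if it is substantial, health-authority approvals described in section 10.1.1. Beyond that, it means already scheduled visits for a few more patients.

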## 10.1.1. Regulatory and Ethical Considerations

• This study will be conducted in accordance with the protocol and with the following:

© 2015-2021 TransCelerate BioPharma

Doc. No. CT 2.01.01. Valid from 31 Jan 2022. Only the electronic version is valid.

Page 47 of 65

- Consensus ethical principles derived from international guidelines including the Declaration of Helsinki and Council for International Organizations of Medical Sciences (CIOMS) international ethical guidelines
- Applicable ICH Good Clinical Practice (GCP) guidelines
- Applicable laws and regulations
- The protocol, protocol amendments, ICF, investigator's brochure and other relevant documents must be submitted to an IRB/IEC by the investigator and reviewed and approved by the IRB/IEC before the study is initiated.
- Any amendments to the protocol will require IRB/IEC approval before implementation of changes made to the study design, except for changes necessary to eliminate an immediate hazard to study participants.
- Protocols and any substantial amendments to the protocol will require health authority approval prior to initiation except for changes necessary to eliminate an immediate hazard to study participants.
- The investigator will be responsible for the following, as applicable:
  - Providing written summaries of the status of the study to the IRB/IEC annually or more frequently in accordance with the requirements, policies, and procedures established by the IRB/IEC
  - Notifying the IRB/IEC of SAEs or other significant safety findings as required by IRB/IEC procedures
  - Providing oversight of the conduct of the study at the site and adherence to requirements of 21 CFR, ICH guidelines, the IRB/IEC, European regulation 536/2014 for clinical studies, European Medical Device Regulation 2017/745 for clinical device research, and all other applicable local regulations

#### 10.1.2. Financial Disclosure

The study is Financed by the Regional Health Authorities through the KlinBeForsk program

#### 10.1.3. Informed Consent Process

- The investigator or the investigator's representative will explain the nature of the study, including the risks and benefits, to the potential participant and answer all questions regarding the study.
- Potential participants will be informed that their participation is voluntary. They will be required to sign a statement of informed consent that meets the requirements of 21 CFR 50, local regulations, ICH guidelines, privacy and data protection requirements, where applicable, and the IRB/IEC or study center.

© 2015-2021 TransCelerate BioPharma

Doc. No. CT 2.01.01. Valid from 31 Jan 2022. Only the electronic version is valid.

Page 48 of 65

- The medical record will include a statement that written informed consent was obtained before the participant was enrolled in the study and the date the written consent was obtained. The authorized person obtaining the informed consent must also sign the ICF.
- Participants will be reconsented to the most current version of the ICF(s) during their participation in the study.
- A copy of the ICF(s) must be provided to the participant.

### 10.1.4. Recruitment strategy

All patients diagnosed with primary adrenal insufficiency in the age range 16-70 years of age in Norway during the active study period, will be asked to participate.

#### 10.1.5. Data Protection

- Participants will be assigned a unique identifier by the sponsor when included in the national registry.
- The participant must be informed that their personal study-related data will be used by the sponsor in accordance with local data protection law. The level of disclosure must also be explained to the participant who will be required to give consent for their data to be used as described in the informed consent
- The participant must be informed that their medical records may be examined by Clinical Quality Assurance auditors or other authorized personnel appointed by the sponsor, and by inspectors from regulatory authorities.
- The contract between sponsor and study sites specifies responsibilities of the parties related data protection, including handling of data security breaches and respective communication and cooperation of the parties.
- Information technology systems used to collect, process, and store study-related data are secured by technical and organizational security measures designed to protect such data against accidental or unlawful loss, alteration, or unauthorized disclosure or access.

### 10.1.6. Dissemination of Clinical Study Data

The results will be published in peer-reviewed international journals. Results will also be disseminated to patients, policy makers and the general public.

## 10.1.7. Data Quality Assurance

- All participant data relating to the study will be recorded on printed or electronic CRFs unless transmitted to the sponsor or designee electronically (e.g, laboratory data). The investigator is responsible for verifying that data entries are accurate and correct by physically or electronically signing the CRF.
- The investigator must permit study-related monitoring, audits, IRB/IEC review, and regulatory agency inspections and provide direct access to source documents.

© 2015-2021 TransCelerate BioPharma

Doc. No. CT 2.01.01. Valid from 31 Jan 2022. Only the electronic version is valid.

Page 49 of 65

- Monitoring details describing strategy, including definition of study critical data items
  and processes (e.g., risk-based initiatives in operations and quality such as risk
  management and mitigation strategies and analytical risk-based monitoring), methods,
  responsibilities, and requirements, including handling of noncompliance issues and
  monitoring techniques (central, remote, or on-site monitoring) are provided in the
  monitoring plan.
- The sponsor or designee is responsible for the data management of this study, including quality checking of the data.
- The sponsor assumes accountability for actions delegated to other individuals (eg, contract research organizations).
- Records and documents, including signed ICFs, pertaining to the conduct of this study must be retained by the investigator for 15 years after study completion unless local regulations or institutional policies require a longer retention period. No records may be destroyed during the retention period without the written approval of the sponsor. No records may be transferred to another location or party without written notification to the sponsor.

